7.2.1 Research Electronic Data Capture (REDCap)

REDCap (<http://project-redcap.org/>), assists with the collection and management of data for diverse clinical and translational research studies. REDCap was designed around the concept of giving research teams an easy method to specify project needs and rapidly develop secure, web-based applications for collection, management and sharing of research data. REDCap accomplishes these key functions through use of a single study metadata table referenced by presentation-level operational modules. Based on this abstracted programming model, databases are developed in an efficient manner with little resource investment beyond the creation of a single data dictionary. The concept of metadata-driven application development is well established, and the critical factor for successful data collection lies in creating a simple workflow methodology allowing research teams to autonomously develop study-related metadata in an efficient manner. Both products include secure institutional data hosting and include full audit-trails in compliance with Health Insurance Portability and Accountability Act (HIPAA) security requirements. The REDCap Consortium is comprised of 647 active institutions. The REDCap currently supports 68,000 projects with over 89,000 users spanning numerous research focus areas across the consortium. The current project will use this software application for the design of electronic forms to collect information from study participants, to link the baseline data, sample collection date, and laboratory results in an automated database family, to perform data cleaning and data quality assurance efficiently, and to design an analytical dataset for the analysis of the project data.

Data will be entered into the REDCap database by members of the study team from Duke, Boston Medical Center, and Cincinnati Children's Hospital using the paper case report forms utilized to record data collected as part of study procedures. Study investigators will be responsible for assuring that all paper records are securely stored according to the requirements of their IRBs. The study investigators will be responsible for assuring the accuracy of the data entered from the paper forms into REDCap. Only the assigned identifiers will be used in REDCap. Therefore, personal health identifiers will not appear in the REDCap database.

In order to perform data cleaning and data quality assurance efficiently, numerous built-in filters and checks for consistency of the data including range and limit checks, branching logic and pull down menus to limit choices for categorical variables to a pre-specified list will be implemented and performed automatically to minimize data entry error. The data will be randomly sampled and checked against source records on a regular basis. The data and related analytical datasets will also be stored at the lead and contributing sites with secured password-protected computers.

7.3 Role of the CDC Investigators in the Project

This study is funded by a CDC contract with Duke University and Boston University as Task Orders in the CISA Project Contract. The Duke University PI ([name]) will oversee the study in partnership with the Boston University PI ([name]). Boston University has a subcontract with Cincinnati Children's Hospital (PI [name]). CDC staff will collaborate with both sites to develop the protocol, conduct the study, ensure the study is aligned with US Department of Health and Human Services (CDC) public health priorities, and analyze the data and disseminate the results. CDC may receive access to coded data not containing any directly identifying information.

8 HUMAN SUBJECTS

8.1 Human Subjects Involvement, Characteristics, and Design

Duke, Boston University, and Cincinnati Children's Hospital investigators will be responsible for submitting the protocol, informed consent (Appendix A), diaries (Appendix E), recruitment letters (Appendix M), flyers (Appendix N), and any written or verbally conveyed materials (Appendix O) specific to this project to their institutional review boards. CDC staff will be responsible for submitting materials to the CDC for Human Subjects review and approval.

To facilitate subject recruitment at the practices, we will request a waiver of consent and HIPAA authorization for ascertainment (identification, selection) and/or recruitment of potential subjects while recording identifiable private health information (PHI) prior to obtaining the subject's consent. This information will be obtained from review of the electronic scheduling and medical record systems in the clinics in order to determine eligibility for study enrollment. We will review only the minimum amount of information necessary to determine eligibility, i.e. date of birth, medical and surgical history, and recent laboratory test results. The PHI collected prior to consent will be used to recruit and screen only. Use of PHI in this manner involves no more than minimal risk to subjects and no information will leave the study sites.

Requests for continuing review, when required, will be submitted at each engaged institution in accordance with institutional procedures. Protocol deviations or concerns about study integrity will be reported promptly to the overseeing IRB or CDC in accordance with institutional requirements.

8.2 Sources of Material

Medical history and immunization history will be obtained from the medical record and from patient report. Demographic information will be obtained from the medical record and patient report. Subjects will record solicited adverse reactogenicity events and any medical intervention sought on study days 1-8 on the symptom diary (Appendix E). Diary information will be reported to the study team during a telephone call. The research staff will assess one or more of the following: weight, height, temperature, blood pressure, and pulse.

8.3 Potential Risks and Benefits

IIV3 or IIV-HD3 are FDA-licensed vaccines approved for use in adults ≥ 65 years old. Both vaccines are standard clinical practice and recommended by the CDC. Participants will be provided with the CDC Vaccine Information Statement (VIS) for IIV (<https://www.cdc.gov/vaccines/hcp/vis/vis-statements/flu.pdf>).

IIV risks include minor problems such as soreness, redness, swelling, or pain where the shot was given, hoarseness, sore, red or itchy eyes, cough, fever, aches, headache, itching, fatigue, all of which usually occur within 1-2 days of vaccination and are self-limiting. Some people get severe pain in the shoulder and have difficulty moving the arm where a shot was given. This happens very rarely. Syncope (fainting) can occur in association with administration of injectable vaccines. Sitting or lying down for about 15 minutes can help prevent fainting, and injuries caused by a fall, as recommended in the ACIP General Recommendations on Immunization¹. Subjects should inform their doctor should they feel dizzy, or have vision changes or ringing in the ears. More serious problems including a small increased risk of Guillain-Barré Syndrome estimated at 1 or 2 additional cases per million people vaccinated. This is much lower than the risk of severe complications from influenza infection, which can be prevented by IIV³⁸. In addition, any medication can cause a severe allergic reaction, or anaphylaxis, which is estimated at ~ 1 in one million doses of IIV administered³⁹.

Risks of blood drawing include pain, swelling, bleeding, or bruising at the site where the blood sample is collected. Subjects may also experience dizziness or fainting. There is a small risk of infection around the vein where the blood was collected. Each study subject will be asked to have up to 3 blood samplings with the total volume not to exceed 30mL over approximately 6 month period of time. Participants who return for repeat vaccination in the second year will be asked to have 2 additional blood sampling with the volume in the second year not to exceed 20 mL.

As with any licensed vaccine, protection may not occur in 100% of vaccinated persons.

An additional risk of study participation is the potential for loss of confidentiality.

8.4 Adequacy of Protection Against Risks

8.4.1 Protections against Risk

To decrease the possibility of infection at the site of blood drawing, the area on the arm above the vein where blood will be taken will be prepped with 70% isopropyl alcohol antiseptic prior to venipuncture.

Subjects will be counseled on possible side effects following vaccination and followed closely during the 8 days post-vaccination for assessment of moderate to severe local or systemic reactogenicity. Subjects will be evaluated and cared for as described in the *Unscheduled Visit* section above. All subjects will be monitored in a sitting or lying position for 15 minutes following vaccinations to help prevent fainting, and injuries caused by a fall. Subjects with a prior history of severe allergic reaction after a previous dose of any influenza vaccine, or to a vaccine component, including egg protein, will be excluded from study enrollment. Data Safety monitoring, as described above (Section 5.4.3 and Appendix H), shall also be done.

The study team will provide documentation to the participant and primary care provider regarding receipt of influenza vaccine without specification of whether it was high dose or adjuvanted vaccine to preserve blinding.

If a participant's care requires the identity of the vaccine received, blinding will be broken for that patient. At the end of the study, the participants and providers will receive documentation about which vaccine the participant received.

Every effort possible will be made to keep information about participants confidential. Computerized participant information will be kept in password-protected files on secured servers. Paper case report forms will be kept in locked files belonging to the study personnel. Any publications resulting from this work will not contain any identifiable participant information.

8.4.2 *ClinicalTrials.gov* Requirements

The project is registered on *ClinicalTrials.gov* (NCT # NCT03183908).

8.5 Human Subjects

In obtaining and documenting informed consent, the Investigator and study team will comply with the applicable regulatory requirements, Good Clinical Practices, and ethical principles. The written informed consent form must be signed and dated by the study participant prior to initiation of any study activities.

Appendix C: Rowland Universal Dementia Assessment Scale (RUDAS)

Appendix D: Treatment Administration Record/Immediate Reactogenicity Assessment Form

Appendix E: Patient Symptom Diary

Appendix F: FACES Pain Scale

Appendix G: Immune-Mediated Conditions

Gastrointestinal disorders
 
 • Celiac disease • Crohn’s disease • Ulcerative colitis • Ulcerative proctitis 	
Liver disorders
 
 • Autoimmune cholangitis • Autoimmune hepatitis • Primary biliary cirrhosis • Primary sclerosing cholangitis

Musculoskeletal disorders
 
 • Antisynthetase syndrome • Dermatomyositis • Mixed connective tissue disorder • Polymyalgia rheumatic • Polymyositis • Psoriatic arthropathy • Relapsing polychondritis • Rheumatoid arthritis • Scleroderma, including diffuse systemic form and CREST syndrome • Spondyloarthritis, including ankylosing spondylitis, reactive arthritis (Reiter's Syndrome) and undifferentiated spondyloarthritis • Systemic lupus erythematosus • Systemic sclerosis 	
Neuroinflammatory disorders
 
 • Acute disseminated encephalomyelitis, including site specific variants (e.g., non-infectious encephalitis, encephalomyelitis, myelitis, myeloradiculomyelitis) • Cranial nerve disorders, including paralyzes/paresis (e.g., Bell’s palsy) • Guillain-Barré syndrome, including Miller Fisher syndrome and other variants • Immune-mediated peripheral neuropathies and plexopathies, including chronic inflammatory demyelinating polyneuropathy, multifocal motor neuropathy and polyneuropathies associated with monoclonal gammopathy • Multiple sclerosis • Narcolepsy • Optic neuritis • Transverse myelitis • Myasthenia gravis, including Eaton-Lambert syndrome

Metabolic diseases
 
 • Addison’s disease • Autoimmune thyroiditis (including Hashimoto thyroiditis) • Diabetes mellitus type I • Grave's or Basedow’s disease 	
Skin disorders
 
 • Alopecia areata • Autoimmune bullous skin diseases, including pemphigus, pemphigoid and dermatitis herpetiformis • Cutaneous lupus erythematosus • Erythema nodosum • Erythema multiforme • Morphoea • Lichen planus • Psoriasis • Sweet’s syndrome • Vitiligo

Vasculitides
 
 • Large vessels vasculitis including: giant cell arteritis such as Takayasu’s arteritis and temporal arteritis 	
Others
 
 • Antiphospholipid syndrome • Autoimmune hemolytic anemia • Autoimmune glomerulonephritis (including IgA nephropathy, glomerulonephritis rapidly

 • Medium sized and/or small vessels vasculitis including: polyarteritis nodosa, Kawasaki's disease, microscopic polyangiitis, Wegener's granulomatosis, Churg–Strauss syndrome (allergic granulomatous angiitis), Buerger's disease thromboangiitis obliterans, necrotizing vasculitis and anti-neutrophil cytoplasmic antibody (ANCA) positive vasculitis (type unspecified), Henoch-Schonlein purpura, Behcet's syndrome, leukocytoclastic vasculitis 	
progressive, membranous glomerulonephritis, membranoproliferative glomerulonephritis, and mesangioproliferative glomerulonephritis)
 
 • Autoimmune myocarditis/cardiomyopathy • Autoimmune thrombocytopenia • Goodpasture syndrome • Idiopathic pulmonary fibrosis • Pernicious anemia • Raynaud's phenomenon • Sarcoidosis • Sjögren's syndrome • Stevens-Johnson syndrome • Uveitis
---	---

Appendix H: Safety Monitoring Plan

The safety monitoring plan includes 3 types of adverse events described in the Table below. The plan includes two components: an ongoing adverse event case report review, and an interim safety data review with the expert safety panel.

Type A adverse events	Type B adverse events	Type C adverse events

 o Syncope occurring post-vaccination while patient is under clinic observation for Day 1 study activities. o Anaphylaxis within 24 hours of vaccination o Guillain-Barré syndrome (GBS) occurring within 42 days of vaccination o Death within 42 days following vaccination 	
 o Serious adverse events (SAE) occurring within 42 days of vaccination, unless unrelated to vaccine o New onset immune-mediated diseases occurring within 42 days of vaccination other than GBS (Appendix G), unless unrelated to vaccine 	
 o Severe injection-site reactions occurring within 7 days of vaccination (Table 2) o Severe fever occurring within 7 days of vaccination (Table 3)

Ongoing AE case report review will be performed as follows:

- A site identifying a Type A AE in a study subject should notify study investigators at both sites and CDC within one business day of identifying the AE. Site investigators should make an assessment as to relatedness to study product (related, possibly related, unlikely related or unrelated) and provide this information when available, but should not delay reporting.
- A site identifying a Type B AE should make an assessment as to relatedness to study product before reporting it. An SAE that is considered to be related or possibly related to vaccine should be reported to study investigators at both sites and CDC within one business day of making this relatedness determination. Type B AEs that are not related do not need to be urgently reported.
- Type C AEs do not need to be reported as part of ongoing monitoring, unless they also result in an SAE.

Information about AE case reports that is shared with the study teams will be blinded with respect to vaccine product used. Reporting to the respective IRB will be per the respective institutional IRB requirements and will also initially be blinded. Sites will provide narrative case reports for Type A AEs and Type B AEs (unless unrelated to vaccine) to CDC within 1 week. No personal identifiable information (PII), including date of vaccination, should be included. Discussions about AE case reports for Type A and B events will take place on routine or ad hoc calls with the study investigators and team. If a site or CDC have clinical safety concerns that they feel need more urgent attention, then the study team will meet promptly to determine a plan of action, which might include consultation with the safety monitoring panel. The following events should lead to a prompt study team meeting:

- If there are 3 or more Type A syncope events
- If there are 2 or more other Type A AEs

- If there are 2 or more other serious AEs or new onset autoimmune diseases (unless unrelated to the study vaccine) that are clinically similar (e.g. same organ class)
- If a clinical investigator involved with the study has a safety concern not specified above that he/she feels needs prompt attention.

The interim safety data review will provide an opportunity to make changes to the protocol or consent before the second year of influenza study enrollment. This data review will include either the first 200 subjects vaccinated with the opportunity for 42 days of follow-up OR all subjects vaccinated with 42 days of follow at the time the report is prepared. This review will include all randomized subjects who received vaccine, including those with protocol violations or who dropped out or died. The review will maintain blinding and will describe the following in aggregate and will also be stratified into two age groups: 65-79 and ≥ 80 years.

- Proportion of each Type A AE (all, related, possibly related, unlikely related or unrelated)
- Proportion of serious AEs (including any Type A AEs also considered serious) (all, related, possibly related, unlikely related, or not related)
- Proportion new immune-mediated diseases (except GBS) (all, related, possibly related, unlikely related, or not related) (Appendix G)
- Proportion of each severe injection-site reaction (Table 2) and severe fever (assume all related)

The interim review will include clinical summary line lists for the AEs described above, except for the reactogenicity events. An appendix of clinical narratives for all Type A and Type B AEs will also be included. The Duke statistical team in collaboration with the study team will prepare and present this summary. Background information about reactogenicity frequencies from the package inserts will be provided. This information will be shared and reviewed with the expert safety panel. The safety panel will consider any concerning findings and determine if there is need to consider additional actions including statistical analyses and reassessment, changes to study eligibility or procedures to minimize or assess risk, or addition of information to the informed consent. The safety panelists will provide individual expert input but will not make final decisions. There are no pre-specified statistical criteria to guide decisions; rather clinical judgement will be used. For all of these steps study investigators and the safety panel will see the same data. The safety panel may make any of the following suggestions at the end of the interim data review.

- No substantial safety concerns and either:
 - No further analysis and continue routine safety monitoring
 - There are some small changes recommended in routine monitoring such as adding a new AE.
- Specific safety concern:
 - If there is a specific safety concern, such as a higher than expected proportion of severe fever after vaccine, than the first step will be to clinically describe the AEs without breaking randomization or blinding. For example, the duration of the fever could be assessed and the level of medical utilization.
 - If after in-depth clinical review, a concern remains, then the next step will be to break randomization into treatment groups (while maintaining blinding). If there is an isolated concern, then it may be sufficient to do this only for the specific AE. For example, if there are 5 SAEs of kidney failure and after breaking into two groups, no imbalance is seen, that may be sufficient.

- If it is clinically needed, then blinding may be broken either for a selected AE or for the full interim data.
- Substantial safety concerns:
 - The interim safety dataset will be analyzed by vaccination group and blinding will be discontinued for these data.

The safety panel will consist of three to four expert physicians who are not investigators on this study. The physicians will consist of staff from the CDC and from CISA site(s) other than Duke or BMC, including at least one internal medicine physician. The panel will meet initially before study enrollment to review the study and the monitoring plan and to share background information about what is known about aIV and IIV3-HD safety (package insert review). A meeting will be scheduled in 2018 for an interim review of safety data. Study investigators and statisticians will be invited to participate, and the meetings will consist of open discussions between the panel and study investigators (under CISA confidentiality agreement). Ad hoc meetings will be scheduled as needed.

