most common moderate/severe injection-site reaction was pain (4.2% aIIV3 and 4% IIV3-HD) and the most common moderate/severe systemic reaction was malaise/fatigue (3.5% aIIV3 and 6.3% IIV3-HD)^{13,18}. These rates of moderate/severe reactions are higher than those reported for IIV3-SD. Moderate/severe reactions are generally those which limit or prevent usual daily activities. For older persons, the ability to independently perform basic activities of daily living (e.g., bathing, dressing, grooming, toileting, eating, mobility) and instrumental activities of daily living (e.g., cooking, housework, traveling, managing money, managing medications) are critical to quality of life. Any reaction that limits or prevent these activities will have a significant impact on health-related quality of life and is likely to be more clinically important than in younger, healthier populations¹⁹⁻²¹.

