Participants will also be queried during Visit 3 on common post-injection systemic symptoms as described in Table 3. Participants will also be encouraged to report any significant unsolicited adverse events in an open-ended question format, e.g. “How are you doing? Are you having any new issues since we saw you last? If so, please tell me about them.” Unsolicited adverse events will be graded as described in Table 4. Participants who report severe solicited adverse events or express any concern about symptoms/unsolicited events will be encouraged to follow up with their primary care provider. Study staff will assist with coordination of referral appointments as necessary. Medical records will be obtained and reviewed for any unscheduled medical appointment through post-vaccination Day 43.

Table 3. Solicited Systemic Reactogenicity

Systemic	Mild (Grade 1)	Moderate (Grade 2)	Severe (Grade 3)
Fever (° C) (° F)	≥37.5 - ≤38.0 ≥99.5 - ≤100.4	>38.0 - ≤39.0 >100.4 - ≤102.2	>39.0 >102.2
Chills	Noticeable with no limitation in normal daily activity	Some limitation in normal daily activity	Completely unable to perform normal daily activity
Fatigue	Noticeable with no limitation in normal daily activity	Some limitation in normal daily activity	Completely unable to perform normal daily activity
Malaise	Noticeable with no limitation in normal daily activity	Some limitation in normal daily activity	Completely unable to perform normal daily activity
Myalgia	Noticeable with no limitation in normal daily activity	Some limitation in normal daily activity	Completely unable to perform normal daily activity
Arthralgia	Noticeable with no limitation in normal daily activity	Some limitation in normal daily activity	Completely unable to perform normal daily activity

Systemic	Mild (Grade 1)	Moderate (Grade 2)	Severe (Grade 3)
Nausea	Noticeable with no limitation in normal daily activity	Some limitation in normal daily activity	Completely unable to perform normal daily activity
Vomiting	Noticeable with no limitation in normal daily activity	Some limitation in normal daily activity	Completely unable to perform normal daily activity
Diarrhea	Noticeable with no limitation in normal daily activity	Some limitation in normal daily activity	Completely unable to perform normal daily activity
Headache	Noticeable with no limitation in normal daily activity	Some limitation in normal daily activity	Completely unable to perform normal daily activity

Table 4 Unsolicited Adverse Events

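### The one scheduled interim safety review tabulates every severe injection-site reaction but, of the ten solicited systemic reactions, only severe fever

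*Combined protocol and SAP*

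**What the plan says.** Section 5.4 solicits five injection-site reactions (Table 2) and ten systemic reactions, under "Table 3. Solicited Systemic Reactogenicity". Apart from fever, which is graded by temperature, each systemic reaction is grade 3 when the person is "Completely unable to perform normal daily activity". Table 2 uses the same definition for injection-site pain, tenderness and shoulder pain. Section 5.4.1.2 treats all Table 3 symptoms as related to vaccine, with no causality assessment.

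Appendix H defines Type C events by two entries: "Severe injection-site reactions occurring within 7 days of vaccination (Table 2") and "Severe fever occurring within 7 days of vaccination (Table 3"). The fourth item of the interim safety review repeats that pair: "Proportion of each severe injection-site reaction (Table 2) and severe fever (assume all related"). The other three items are Type A events, serious adverse events and new immune-mediated diseases. The review covers "the first 200 subjects vaccinated with the opportunity for 42 days of follow-up" or, alternatively, everyone with 42 days of follow-up when the report is prepared. It is blinded, in aggregate and by two age groups. Its stated use is to allow changes to the protocol or consent before the second season. One such review is scheduled, in 2018.

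Section 1.1 reports that "the most common moderate/severe systemic reaction was malaise/fatigue (3.5% aIIV3 and 6.3% IIV3-HD"), citing the two package inserts. It adds: "Any reaction that limits or prevent these activities will have a significant impact on health-related quality of life".

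**The concern.** The interim list treats two kinds of event differently although the plan grades them alike. A person kept from all normal activity by a sore shoulder is counted for the panel. A person kept from all normal activity by malaise or myalgia is not, unless the event meets a seriousness criterion or someone brings it forward. Relatedness does not explain the difference, because all Table 3 symptoms are taken as related. Nor does rarity, because the most common moderate/severe systemic reaction that the protocol cites is malaise/fatigue, not fever.

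At stake is what the panel has in front of it at the one planned point where the protocol or consent can be changed between seasons. Appendix H also supplies the panel with package-insert reactogenicity frequencies as background. For nine of the ten systemic reactions the panel would have no trial count to set beside them.

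**Working it through.** The plan states no figure for this point, so there is none to reproduce. The check is a count, followed by arithmetic for scale.

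**1. Coverage of solicited reactions**

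| Source | Solicited (Section 5.4) | In Type C and interim item 4 | Left out |
|---|---|---|---|
| Table 2, injection site | 5 (pain, tenderness, shoulder pain, induration/swelling, erythema/redness) | 5 | 0 |
| Table 3, systemic | 10 (fever, chills, fatigue, malaise, myalgia, arthralgia, nausea, vomiting, diarrhea, headache) | 1 (fever) | 9 |
| Total | 15 | 6 | 9 |

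**2. Where a severe non-fever systemic reaction falls in Appendix H**

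- Type A: no. That list is syncope under observation, anaphylaxis, Guillain-Barré syndrome and death.
- Type B: only if it is also a serious adverse event or a new immune-mediated disease, and not judged unrelated.
- Type C: no.
- Interim tables: only through the serious adverse event line.

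Inability to carry out normal activities for a day or so need not meet any seriousness criterion in Section 5.4.2.

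**3. Subjects vaccinated after Year 1** (Section 4.3, approximate targets)

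- Year 1: 220 (Duke) + 170 (Boston) = 390.
- Year 2: 220 + 170 + 100 (Cincinnati) = 490.
- Share in Year 2: 490 / 880 = 56%, plus up to 60 Year 1 subjects at Duke who are revaccinated.

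**4. What 200 subjects would contain**

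Moderate/severe malaise/fatigue, at the rates quoted in Section 1.1:

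- 200 × 0.035 = 7.0
- 200 × 0.063 = 12.6

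That is about 7 to 13 people, moderate and severe together. The documents give no severe-only rate, so the next table rests on assumed rates p for one given symptom. The chance of at least one case is 1 − (1 − p)^200.

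| Assumed severe rate | Expected in 200 | Chance of at least one |
|---|---|---|
| 0.5% | 1 | 63% |
| 1% | 2 | 87% |
| 2% | 4 | 98% |

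**5. Effect of the change**

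Solicited reactions in the interim table rise from 6 (5 + 1) to 15 (5 + 10), plus one summary row.

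**The case against.** The best defence is that a short interim list is a legitimate choice. Both vaccines are licensed, Section 5.4.3 says the monitoring plan aims to limit investigator burden, and nothing in the documents promises interim tables of every Table 3 item. All these reactions are compared at study end under Secondary Objective 1, including by age group. This stands. The omission contradicts no other part of the plan, and no final analysis is damaged.

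Four stronger readings are tempting, and the documents do not support them.

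- *That the protocol ranks systemic reactions as the most important clinically.* Section 1.1 calls malaise/fatigue the most common moderate/severe systemic reaction. Its remark on clinical importance covers any activity-limiting reaction and compares older with younger, healthier people. It does not place systemic above local reactions, and Primary Objective 1 concerns injection-site pain.
- *That these events can never reach the panel.* The interim review includes all serious adverse events whatever their relatedness. An investigator's unlisted concern should lead to a prompt team meeting, which might consult the panel. Ad hoc meetings are allowed, and the panel may suggest adding an event to routine monitoring. However, apart from the serious-event line, these routes depend on someone noticing a pattern that nobody is assigned to tabulate.
- *That the nine are uniquely missing from ongoing reports.* Type C events are not reported there either, unless they result in a serious adverse event. The gain is confined to the interim table.
- *That the panel would see an excess for one vaccine.* The table is pooled and blinded, and should stay so. It could show only an overall or age-group rate above expectation. Such a finding could start Appendix H's own stepwise follow-up, which proceeds from clinical description to splitting by group if concern remains.

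**Conclusion.** The gap is real but modest. Type C and the one scheduled interim review cover 5 of 5 severe injection-site reactions and 1 of 10 severe systemic reactions, with no reason given. The other nine are not routinely tabulated for the panel unless serious or raised ad hoc, although they are taken as vaccine-related and share the grade 3 definition of the tabulated pain items.

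The count of nine rests on the documents alone. The 490 and 56% rest on approximate site targets. The expectation of about 1 to 4 severe cases of a given symptom in 200 subjects rests on assumed rates of 0.5% to 2%. It would scale up if the review used all Year 1 subjects with 42 days of follow-up. The change is worth making because it is cheap and serves the stated purpose of the review, not because the documents show that a signal would be missed.

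**What to change.** In Appendix H, reword the Type C entry and the fourth item of the interim review to read: *each severe injection-site reaction (Table 2) and each severe systemic reaction (Table 3) within 7 days of vaccination*. Add one row for any severe systemic reaction. Present all rows pooled, blinded and by the two age groups, beside the package-insert frequencies already planned. If the sponsor prefers to keep fever alone, Appendix H should state why.

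The cost is one wording change and about ten more rows in one table (nine reactions plus the summary row). The diary and the Visit 3 review already collect and grade these data. No unblinding and no alpha is involved, and no clinical rule changes. The downside is a slightly longer interim report.
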